2.8 Safety analyses

For all safety analyses, the safety set will be used. All listings and tables will be presented by treatment group.

There is no formal safety hypotheses in this study. All safety analyses will be descriptive.

The safety analysis will include all treatment-emergent data, i.e., data collected after the start of the study treatment.

2.8.1 Adverse events (AEs)

A treatment-emergent AE is defined as any AE that develops after initiation of the study treatments or any event already present that worsens following exposure to the study treatment.

All information obtained on adverse events will be displayed by treatment group and participant.

The number (and percentage) of participants with treatment-emergent adverse events (events started after the first dose of study medication or events present prior to start of double-blind treatment but increased in severity based on preferred term) will be summarized in the following ways:

- by treatment, primary system organ class and preferred term.

- by treatment, primary system organ class, preferred term and maximum severity.

Adverse events reported will be sorted alphabetically by primary system organ class and then in descending frequency according to its incidence in the HCQ+AZI. For ties in incidence rate of HCQ group, sort adverse event by incidence rate of HCQ. A participant with multiple adverse events within a primary system organ class is only counted once towards the total of the primary system organ class. If a particular AE 'severity' is missing, this variable will be listed as missing and treated as missing in summaries. If a participant reported more than one adverse event with the same preferred term, the adverse event with the greatest severity will be presented. If a participant reported more than one adverse event within the same primary system organ class, the participant will be counted only once with the greatest severity at the system organ class level, where applicable.

Separate summaries will be provided for study medication related adverse events, death, serious adverse events, other significant adverse events leading to discontinuation.

Algorithms for date imputations are provided in [Section 5.1.2](#).

For serious adverse events (SAEs) occurred during screening a listing will be prepared for all participants screened including screening failures.

The MedDRA version used for reporting the study will be described in a footnote.

2.8.1.1 AE reporting for CT.gov and EudraCT

For the legal requirements of clinicaltrials.gov and EudraCT, two required tables on treatment emergent adverse events which are not serious adverse events with an incidence greater than 2% and on treatment emergent serious adverse events and SAE suspected to be related to study treatment will be provided by system organ class and preferred term on the safety set population.

If for the same participant, several consecutive AEs (irrespective of study treatment causality, seriousness and severity) occurred with the same SOC and PT:

- a single occurrence will be counted if there is ≤ 1 day gap between the end date of the preceding AE and the start date of the consecutive AE
- more than one occurrence will be counted if there is > 1 day gap between the end date of the preceding AE and the start date of the consecutive AE

For occurrence, the presence of at least one SAE/SAE suspected to be related to study treatment / non SAE has to be checked in a block e.g., among AE's in a ≤ 1 day gap block, if at least one SAE is occurring, then one occurrence is calculated for that SAE.

The number of deaths resulting from SAEs suspected to be related to study treatment and SAEs irrespective of study treatment relationship will be provided by SOC and PT.

2.8.2 Deaths

The primary causes of death may be attributable to complication of COVID-19 disease or any other reasons.

Deaths will be listed.

2.8.3 Laboratory data

Laboratory samples will be taken at screening, Day 4, Day 10 and at the Day 15 visit. Laboratory tests will be conducted by a local lab. For hematology, biochemistry and urinalysis parameters, sites will be asked to only provide results in case the lab results was abnormal (i.e. normal lab results may not be collected on the local CRF page).

All results of inflammatory markers will be collected in the CRF where possible.

2.8.3.1 Standard data summaries

[REDACTED]

[REDACTED]

For the list of parameters provided in [Section 5.3.1](#), the number (percentage) of participants with at least one newly occurring or worsening lab abnormality during study will be presented by laboratory test and CTCAE grade value. For a given test, the lab results with maximum severity will be reported.

Laboratory results marked as grade 3 or grade 4 will be listed by treatment group, participant, and visit.

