5.2 Exclusion criteria

Participants meeting any of the following criteria are not eligible for inclusion in this study.

1. Use of other investigational drugs within 5 half-lives or 30 days of enrollment whichever is longer
2. Participation in any other clinical trial of an experimental treatment for COVID-19 within 5 half-lives or 30 days of enrollment whichever is longer
3. Expectation of concurrent treatment with other agents with actual or potential direct acting antiviral activity against SARS-CoV-2 during study drug dosing period, including but not limited to oseltamivir and protease inhibitors
4. History of hypersensitivity to any of the study treatments or its excipients or to drugs of similar chemical classes.

5. Requires, in the judgement of the investigator, admission to the intensive care unit (ICU) or mechanical ventilatory support (invasive or non-invasive) prior to the initiation of study drug
(There might be a participant who cannot be admitted to the ICU, even if the participant's condition is severe enough, due to administrative reasons under the current circumstances. This case is also considered under admission to the ICU judged by the investigator)
6. Evidence of cytokine storm syndrome or multi-organ system failure
7. Confirmed co-infection with influenza
8. Creatinine clearance < 45 mL/min or requiring acute renal replacement therapy
9. History or current diagnosis of ECG abnormalities indicating significant risk of safety for participants participating in the study such as:
 - Concomitant clinically significant cardiac arrhythmias, e.g. sustained ventricular tachycardia, and clinically significant second or third degree AV
 - History of familial long QT syndrome or known family history of Torsades de Pointe
 - QTcF > 480 msec (at screening and/or Day 1 at pre-dose) based on the local ECG data
 - Uncorrected electrolyte abnormalities, such as hypokalemia, hypomagnesemia and hypocalcemia
 - Use of agents known to prolong the QT interval within 5 half-lives before screening
10. Any other condition (e.g. known liver disease) which, in the opinion of the investigator, would put the safety of the participant at risk, impede compliance or hinder completion of the study
11. Pregnant or nursing (lactating) women

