8.4.3 Laboratory evaluations

Laboratory test will be conducted as per [Table 8-1](#) by local lab. Details on the parameters are listed below in [Table 8-2](#).

Clinically significant abnormal results for hematology, chemistry and urinalysis will be reported in the laboratory results CRF and as an AE, otherwise all these results will be kept in the source documents and will not need to be recorded in CRF. [REDACTED]

Table 8-2 Laboratory parameters (local lab)

Test Category	Test Name
Hematology	Hematocrit, hemoglobin, platelets, red blood cells, white blood cells (WBC), absolute differential WBC count (basophils, eosinophils, lymphocytes, monocytes, neutrophils, bands, other)
Chemistry	Alkaline phosphatase, alanine transaminase (ALT), aspartate aminotransferase (AST), calcium, magnesium, potassium, creatinine, direct bilirubin, total bilirubin, blood urea nitrogen (BUN), glucose, troponin (I or C as available), CPK
Urinalysis (dipstick)	Specific gravity, pH, protein, glucose and blood
Pregnancy Test	Serum / Urine pregnancy test
[REDACTED]	[REDACTED]

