10.2 Additional Safety Monitoring

10.2.1 Cardiac safety monitoring

In case of QTcF > 500 msec and QTcF prolongation > 60 msec from baseline, please take the following steps:

- Temporarily interrupt study treatment
- Assess the quality of the ECG recording and the QT value and record two additional ECG tracings to confirm the values
- Determine the serum electrolyte levels (in particular hypokalemia, hypomagnesemia and/or hypocalcemia). If abnormal, correct abnormalities before resuming study treatment.
- Review concomitant medication use for other causes for QT prolongation (refer to qt drugs.org for known QT prolonging drugs) and for drugs with the potential to increase the risk of drug exposure of study drugs
- Check the dosing schedule and treatment compliance
- Increase cardiac monitoring as indicated, (consider continuous telemetry monitoring) until the QTcF returns to ≤ 480 msec
- If QTcF is ≤ 480 msec prior to the next dose, continue dosing with another ECG collected 4 hrs post dose
- If QTcF remains > 480 msec prior to the next dose discontinue study treatment for the participant permanently

In case of persistent QTcF > 500 msec and QTcF prolongation > 60 msec from baseline and/or documented new onset arrhythmia (e.g. Torsade de Pointes, Ventricular Tachycardia) or syncope - discontinue treatment for the participant and request evaluation by a cardiologist.

Please refer to [Appendix 1](#) for notable vital signs.

Local practices should be followed to ensure participant safety for Liver and Renal monitoring, in addition below are suggested guidelines for safety monitoring.

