5.3 Safety derivations

5.3.1 Laboratory parameters derivations

CTCAE grade for the laboratory parameters assess in the trial are provided in [Table 5-1](#).

Table 5-1 CTCAE grades for laboratory parameters (CTCAE Version 5.0)

		Grade			
Abnormality	Lab parameter	1	2	3	4
Hematology					
Anemia	Hemoglobin (g/L)	<LLN - 100 g/L	<100 - 80 g/L	<80 g/L; transfusion indicated	Life-threatening consequences; urgent intervention indicated
Platelet count decreased	Platelets (thrombocytes) (10 ⁹ /L)	<LLN-75.0 x 10 ⁹ /L	<75.0 - 50.0 x 10 ⁹ /L	<50.0 - 25.0 x 10 ⁹ /L	<25.0 x 10 ⁹ /L
White blood cell decreased	Leukocytes (WBCs) (10 ⁹ /L)	<LLN - 3.0 x 10 ⁹ /L	<3.0 - 2.0 x10 ⁹ /L	<2.0 - 1.0 x 10 ⁹ /L	<1.0 x 10 ⁹ /L
Neutrophil count decreased	Absolute neutrophil count (10 ⁹ /L)	<LLN - 1.5 x10 ⁹ /L	<1.5 - 1.0 x10 ⁹ /L	<1.0 - 0.5 x10 ⁹ /L	<0.5 x10 ⁹ /L

		Grade			
Abnormality	Lab parameter	1	2	3	4
Lymphocyte count decreased	Absolute lymphocyte count (10 ⁹ /L)	<LLN x 0.8 - 10 ⁹ /L	<0.8 - 0.5 x 10 ⁹ /L	<0.5 - 0.2 x 10 ⁹ /L	<0.2 x 10 ⁹ /L
Lymphocyte count increased	Absolute lymphocyte count (10 ⁹ /L)		>4 – 20 x 10 ⁹ /L	> 20 x 10 ⁹ /L	
Chemistry					
Liver function					
Alanine aminotransferase increased	ALT (SGPT) (U/L)	ULN - 3.0 x ULN if baseline was normal; 1.5 - 3.0 x baseline if baseline was abnormal	>3.0 - 5.0 x ULN if baseline was normal; >3.0 - 5.0 x baseline if baseline was abnormal	>5.0 - 20.0 x ULN if baseline was normal; >5.0 - 20.0 x baseline if baseline was abnormal	>20.0 x ULN if baseline was normal; >20.0 x baseline if baseline was abnormal
Aspartate aminotransferase increased	AST (SGOT) (U/L)	>ULN - 3.0 x ULN if baseline was normal; 1.5 - 3.0 x baseline if baseline was abnormal	>3.0 - 5.0 x ULN if baseline was normal; >3.0 - 5.0 x baseline if baseline was abnormal	>5.0 - 20.0 x ULN if baseline was normal; >5.0 - 20.0 x baseline if baseline was abnormal	>20.0 x ULN if baseline was normal; >20.0 x baseline if baseline was abnormal
Blood bilirubin increased	Bilirubin (µmol/L)	>ULN - 1.5 x ULN if baseline was normal; > 1.0 - 1.5 x baseline if baseline was abnormal	>1.5 - 3.0 x ULN if baseline was normal; >1.5 - 3.0 x baseline if baseline was abnormal	>3.0 - 10.0 x ULN if baseline was normal; >3.0 - 10.0 x baseline if baseline was abnormal	>10.0 x ULN if baseline was normal; >10.0 x baseline if baseline was abnormal

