GGT increased	Gamma-glutamyl transferase (GGT) (U/L)	>ULN - 2.5 x ULN if baseline was normal; 2.0 - 2.5 x baseline if baseline was abnormal	>2.5 - 5.0 x ULN if baseline was normal; >2.5 - 5.0 x baseline if baseline was abnormal	>5.0 - 20.0 x ULN if baseline was normal; >5.0 - 20.0 x baseline if baseline was abnormal	>20.0 x ULN if baseline was normal; >20.0 x baseline if baseline was abnormal
Alkaline phosphatase increased	Alkaline Phosphatase (U/L)	>ULN - 2.5 x ULN if baseline was normal; 2.0 - 2.5 x baseline if baseline was abnormal	>2.5 - 5.0 x ULN if baseline was normal; >2.5 - 5.0 x baseline if baseline was abnormal	>5.0 - 20.0 x ULN if baseline was normal; >5.0 - 20.0 x baseline if baseline was abnormal	>20.0 x ULN if baseline was normal; >20.0 x baseline if baseline was abnormal
Electrolytes					
Hypermagnesemia	Magnesium (Mg)	>ULN - 1.23 mmol/L	-	>1.23 - 3.30 mmol/L	>3.30 mmol/L; life-threatening consequences
Hypomagnesemia	Magnesium (Mg)	<LLN - 0.5 mmol/L	<0.5 - 0.4 mmol/L	<0.4 - 0.3 mmol/L	<0.3 mmol/L; life-threatening consequences
Hypokalemia	Potassium (K)	<LLN - 3.0 mmol/L	Symptomatic with <LLN - 3.0 mmol/L; intervention indicated	<3.0 - 2.5 mmol/L; hospitalization indicated	<2.5 mmol/L; life-threatening consequences

Abnormality	Lab parameter	Grade			
		1	2	3	4
Hyperkalemia	Potassium (K)	>ULN - 5.5 mmol/L	>5.5 - 6.0 mmol/L; intervention initiated	>6.0 - 7.0 mmol/L; hospitalization indicated	>7.0 mmol/L; life-threatening consequences
Cardiac abnormalities					
Renal function Note: A semi-colon (;) indicates 'or' within the description of the grade.					
CPK increased	CPK (creatinine phosphokinase)	>ULN - 2.5 x ULN	>2.5 x ULN - 5 x ULN	>5 x ULN - 10 x ULN	>10 x ULN
Creatinine increased	Creatinine (µmol/L)	>ULN - 1.5 x ULN	>1.5 - 3.0 x baseline; >1.5 - 3.0x ULN	>3.0 baseline; >3.0 - 6.0 x ULN	>6.0 x ULN
Metabolism					
Hypoglycemia	Glucose (mmol/L)	<LLN - 55 mg/dL; <LLN - 3.0 mmol/L	<55 - 40 mg/dL; <3.0 - 2.2 mmol/L	<40 - 30 mg/dL; <2.2 - 1.7 mmol/L	<30 mg/dL; <1.7 mmol/L; life-threatening consequences; seizures

Note: summary statistics for laboratory parameters will only be based on laboratory measurements. Therefore the definition of CTCAE grade in these summary may slightly differ from the above definition.

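### SAP Table 5-1 has no calcium row, so calcium abnormalities cannot enter the CTCAE-graded laboratory table or the grade 3/4 listing

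*SAP*

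**What the plan says.** **Outputs.** SAP 2.8.3.1 plans a table, restricted to the parameters in SAP 5.3.1, in which the number and percentage of "participants with at least one newly occurring or worsening lab abnormality during study will be presented by laboratory test and CTCAE grade value". It adds that "Laboratory results marked as grade 3 or grade 4 will be listed by treatment group, participant, and visit".

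**Grades.** SAP 5.3.1 introduces Table 5-1 with the words "CTCAE grade for the laboratory parameters assess in the trial are provided in" that table. Its electrolyte block has four rows: magnesium high and low, and potassium high and low. Its liver block includes GGT.

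**What is measured.** The chemistry row of protocol Table 8-2 (section 8.4.3) includes "aspartate aminotransferase (AST), calcium, magnesium, potassium, creatinine, direct bilirubin, total bilirubin". Footnote 7 of Table 8-1 also includes calcium. GGT is in neither visible list. It appears in the event-driven liver follow-up of protocol 10.2.2 and Appendix 2.

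**Why calcium is named.** The ECG exclusion in protocol 5.2 includes "Uncorrected electrolyte abnormalities, such as hypokalemia, hypomagnesemia and hypocalcemia". For a prolonged QTcF, protocol 10.2.1 tells the site to "Determine the serum electrolyte levels (in particular hypokalemia, hypomagnesemia and/or hypocalcemia".

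**What is recorded.** Protocol 8.4.3 sends clinically significant abnormal chemistry results to the laboratory CRF and also to the AE record; other results stay in source documents. SAP 2.8.3 describes a wider request: sites give hematology, biochemistry and urinalysis results when they are abnormal.

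**Liver enzymes.** SAP 2.8.3.3 says that, because the trial is small, new or worsening liver enzyme abnormalities will not be summarized.

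**The concern.** Table 5-1 decides which analytes can be graded, and both graded outputs depend on it. It is presented as covering what the trial assesses, yet it leaves out a scheduled analyte that the protocol treats as QT-relevant. Protocol 4.5 singles out QT prolongation as the risk most relevant to short-term use of the two drugs, and clinically significant laboratory change is a stated safety endpoint.

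The protocol groups potassium, magnesium and calcium twice in its QT rules. The SAP grades the first two and gives no reason for dropping the third. A reader of the report who sets the QTcF results beside the graded electrolytes would see two of the three, and nothing would show that calcium had been left out rather than found normal.

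**Working it through.** No power, sample-size or alpha calculation enters this point. The check sets the scheduled chemistry panel against the graded list, then traces where a calcium abnormality could appear.

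**Step 1: scheduled against graded chemistry**

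| Analyte | Protocol Table 8-2 | SAP Table 5-1 |
|---|---|---|
| ALT, AST, ALP, total bilirubin | yes | yes |
| Magnesium, potassium | yes | yes (high and low) |
| Creatinine, CPK | yes | yes |
| Glucose | yes | yes (low only) |
| **Calcium** | **yes** | **no** |
| BUN, troponin, direct bilirubin | yes | no |
| **GGT** | **no** | **yes** |

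The single bilirubin row in Table 5-1 is matched here to total bilirubin. The panel has 13 scheduled analytes and Table 5-1 grades 10. Without GGT, 10 − 1 = 9 scheduled analytes are graded, and 13 − 9 = 4 are not. Of those four, only calcium is named in the protocol's QT rules. Of the three electrolytes named there, 2 of 3 are graded.

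**Step 2: where a calcium abnormality can appear**

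| Output | Calcium? | Reason |
|---|---|---|
| New-or-worsening table by CTCAE grade (SAP 2.8.3.1) | no | limited to the 5.3.1 list |
| Grade 3/4 listing (SAP 2.8.3.1) | no | needs a grade, and calcium has none |
| AE tables (SAP 2.8.1) | yes, if clinically significant | protocol 8.4.3 makes it an AE; severity is mild, moderate or severe (protocol 10.1.1), not CTCAE |
| By-visit laboratory summary (SAP 2.1.1.7) | yes, on its wording | chemistry is named as a category; it does not count participants with a new abnormality |
| Redacted text opening SAP 2.8.3.1 | unknown | two paragraphs cannot be read |

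Protocol 12.5.1 planned a flagged listing of all laboratory data and shift tables, which would have covered calcium. The visible text of SAP 2.8.3 does not repeat them.

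**Step 3: size**

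SAP 1.1 gives 20 randomized, including one mis-randomized participant. By the definition in SAP 2.2 that person was not treated, so the safety set is at most 20 − 1 = 19. The documents give no counts by arm. If the arms are nearly equal, 19/3 ≈ 6.3, so each has 6 or 7. One participant with a graded calcium abnormality would then be 1/7 = 14% to 1/6 = 17% of an arm.

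What the extra rows add depends on the recording rule that sites followed:

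- Under protocol 8.4.3, every recorded calcium abnormality is already an AE, and the rows add only a grade and a line in the listing.
- Under SAP 2.8.3, abnormal results not judged clinically significant are also recorded, and the rows give them the only graded output they would have.

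**The case against.** The strongest reply is that little is lost. A clinically significant calcium result is an AE and is tabulated by treatment, system organ class, preferred term and maximum severity. SAP 2.1.1.7 promises by-visit chemistry summaries. QT risk is summarized directly through QTcF thresholds and changes in SAP 2.8.4.1.1. The study was halted and the SAP was deliberately cut down for an abbreviated report. BUN and troponin also lack rows, so picking out calcium is selective. Table 5-1 has also been damaged in extraction (a cardiac heading with no row under it), so a lost row cannot be fully excluded.

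Most of this stands as a limit on size. It does not remove the mismatch. AE severity is not a CTCAE grade, the by-visit summary does not count new or worsening cases, and normal results may not be collected at all (SAP 2.8.3). The protocol itself singles out calcium by naming it with potassium and magnesium in the QT rules. Nothing shows that a calcium row was lost: the visible electrolyte block runs from magnesium to potassium and then to the next heading.

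A reader might infer that calcium abnormalities never reach any safety table. The documents do not support that, because of the AE route, the by-visit wording and the redacted paragraphs. A reader might also infer that the GGT row would produce a misleadingly low percentage. That is not supported either. The documents give no number of liver work-ups, SAP 2.8.3.3 says liver enzyme abnormalities will not be summarized, and a rate among participants tested because of a liver trigger would come from a selected group. A grading row for GGT values that arise in follow-up does no harm in itself.

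**Conclusion.** The point holds in a narrow form. On the visible text, calcium is scheduled and named as QT-relevant, but it cannot enter the CTCAE new-or-worsening table or the grade 3/4 listing, whereas potassium and magnesium can. The effect is small: at most 19 treated participants, descriptive analysis only, and clinically significant cases still visible as AEs without a CTCAE grade. In a trial of this size individual listings carry much of the safety information, so the grade 3/4 listing is the part most worth completing.

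This rests on two assumptions: that Table 5-1 lost no calcium row in extraction, and that the redacted paragraphs do not add calcium to the graded outputs.

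Two secondary inconsistencies are minor. GGT is graded but is not in the visible scheduled panel. SAP 2.8.3.3 also conflicts with SAP 2.8.3.1 and Table 5-1, which would tabulate ALT, AST, ALP and GGT by grade.

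**What to change.** Add hypocalcemia and hypercalcemia rows to SAP Table 5-1, with grades taken from CTCAE version 5.0, so that recorded calcium results enter both the graded table and the grade 3/4 listing. The note under Table 5-1, which says that summaries use laboratory measurements only, would apply to these rows too. If calcium is left out on purpose, say so and give the reason.

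In the same edit, reconcile SAP 2.8.3.3 with 2.8.3.1 by stating whether the liver enzymes are in the graded table. Mark GGT as arising only from event-driven follow-up.

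The cost is two table rows with minor programming, and a sentence or two of text. Calcium is already in the panel, so no new sample or visit is needed.

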2.8.3.2 Serum pregnancy test

Results from serum pregnancy test will not be collected on the CRF.

2.8.3.3 Liver transaminase elevation

Considering the limited number of participants in the trial, newly occurring or worsening liver enzyme abnormalities will not be summarized.

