16.1 Appendix 1: Clinically notable laboratory values and vital signs

Investigators are responsible for reviewing abnormal laboratory values for clinical significance, signing the laboratory reports to indicate their review, and reporting values considered clinically significant in the appropriate eCRF.

Any clinically significant abnormal laboratory value should be evaluated and followed-up by the investigator until normal or a cause for the abnormality is determined.

See [Appendix 2](#) for specific liver event and laboratory test trigger definitions and follow-up requirements.

See [Appendix 3](#) for specific renal alert criteria and actions.

Post-baseline vital signs will be flagged as notable abnormalities as follows:

1. Systolic/Diastolic blood pressure: $\geq 25\%$ decrease or $\geq 25\%$ increase from baseline
2. Pulse: ≥ 110 bpm with $\geq 15\%$ change from baseline, or < 50 bpm with $\geq 15\%$ change from baseline

16.2 Appendix 2: Suggested Liver event and laboratory trigger definitions & follow-up requirements

Table 16-1 Liver event and laboratory trigger definitions

	Definition/ threshold
Liver laboratory triggers If ALT, AST and total bilirubin normal at baseline:	
 ALT or AST > 5 × ULN ALP > 2 × ULN (in the absence of known bone pathology) Total bilirubin > 3 × ULN (in the absence of known Gilbert syndrome) ALT or AST > 3 × ULN and INR > 1.5 Potential Hy's Law cases (defined as ALT or AST > 3 × ULN and Total bilirubin > 2 × ULN [mainly conjugated fraction] without notable increase in ALP to > 2 × ULN) Any clinical event of jaundice (or equivalent term) ALT or AST > 3 × ULN accompanied by (general) malaise, fatigue, abdominal pain, nausea, or vomiting, or rash with eosinophilia Any adverse event potentially indicative of a liver toxicity*
If ALT or AST abnormal at baseline:	
 ALT or AST > 2x baseline or > 300 U/L (whichever occurs first)

*These events cover the following: hepatic failure, fibrosis and cirrhosis, and other liver damage-related conditions; non-infectious hepatitis; benign, malignant and unspecified liver neoplasms ALP: Alkaline phosphatase, ALT: Alanine aminotransferase, AST: Aspartate aminotransferase, ULN: upper limit of normal
	

Table 16-2 Follow up requirements for liver laboratory triggers with liver symptoms

	ALT	TBL	Liver Symptoms	Action
ALT increase without bilirubin increase:				

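### SAP 2.8.3.3 drops the liver enzyme summary that SAP 2.8.3.1 requires, and the grade 3-4 listing that is left can miss a potential Hy's Law case

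*SAP*

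**What the plan says.** SAP 2.8.3.1 (Standard data summaries) takes its parameters from Section 5.3.1 and says that "the number (percentage) of participants with at least one newly occurring or worsening lab abnormality during study will be presented by laboratory test". The table is also split by CTCAE grade. It makes no exception. Table 5-1 in Section 5.3.1 has a liver function block that opens with "Alanine aminotransferase increased" and continues with AST, bilirubin, GGT and ALP.

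SAP 2.8.3.1 then adds: "Laboratory results marked as grade 3 or grade 4 will be listed by treatment group, participant, and visit".

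SAP 2.8.3.3 (Liver transaminase elevation) cites the small number of participants and says that "newly occurring or worsening liver enzyme abnormalities will not be summarized".

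Protocol Appendix 2, Table 16-1, lists liver laboratory triggers. For participants with normal baseline values, a potential Hy's Law case is "ALT or AST > 3 × ULN and Total bilirubin > 2 × ULN", with mainly conjugated bilirubin and without ALP rising above 2 x ULN.

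Protocol 12.5.1 planned to list all laboratory data and to give shift tables from baseline to the worst on-treatment value. SAP Section 1 says analyses were reduced or simplified after the study was halted. SAP Section 4 records no change to the protocol-specified analyses.

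**The concern.** Two sections of the same SAP use the same description of an abnormality and give opposite orders. A programmer must pick one, and nothing stops that choice from being made after the results are known.

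The choice affects what is reported. Clinically significant laboratory change is a stated safety endpoint (Protocol Table 2-1, SAP Table 1-1), and Protocol 10.2.2 sets up liver monitoring to help determine hepatotoxic potential. If 2.8.3.3 is followed, grade 1-2 rises in ALT, AST, GGT and ALP leave both the abnormality table and the listing. The question is then whether the grade 3-4 listing is an adequate substitute for the combined ALT/bilirubin pattern that the protocol itself singles out.

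**Working it through.** The plan gives no figure on this point, so there is nothing to reproduce. The check sets the passages side by side and maps the protocol's thresholds on to the SAP's grades.

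**1. The two instructions**

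| Table 5-1 rows | SAP 2.8.3.1 | SAP 2.8.3.3, read literally |
|---|---|---|
| ALT, AST, GGT, ALP | summarize | do not summarize |
| Bilirubin | summarize | not addressed (not an enzyme) |

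Read by its heading alone, 2.8.3.3 would concern only the transaminases. The conflict would then cover ALT and AST.

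**2. Inputs for the threshold check** (normal baseline, multiples of ULN)

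| Test | Grade 1 | Grade 2 | Grade 3 |
|---|---|---|---|
| ALT, AST | up to 3.0 | >3.0 to 5.0 | >5.0 to 20.0 |
| Bilirubin | up to 1.5 | >1.5 to 3.0 | >3.0 to 10.0 |
| ALP | up to 2.5 | >2.5 to 5.0 | >5.0 to 20.0 |

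The grades are from SAP Table 5-1. The potential Hy's Law rule, from Protocol Table 16-1, is: the higher of ALT and AST > 3, total bilirubin (TBL) > 2, and ALP not above 2.

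**3. When such a case escapes the listing**

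A case is unlisted on these tests if ALT and AST are both ≤ 5 and TBL ≤ 3. ALP ≤ 2 is at most grade 1 and adds nothing. Combining this with the rule gives the missed region:

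- 3 < higher of ALT and AST ≤ 5, and
- 2 < TBL ≤ 3.

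| ALT / TBL (x ULN) | ALT grade | TBL grade | In the grade 3-4 listing? |
|---|---|---|---|
| 3.1 / 2.1 | 2 | 2 | no |
| 4 / 2.5 | 2 | 2 | no |
| 5 / 3 | 2 | 2 | no |
| 5.1 / 2.1 | 3 | 2 | ALT only |
| 3.1 / 3.1 | 2 | 3 | TBL only |
| 6 / 4 | 3 | 3 | both, as separate results |

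**4. Pairing**

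In the fourth and fifth rows the grade 2 partner value is left out, so the pair cannot be seen. In the last row both values appear, but no joint flag is planned. The 2.8.3.1 table, if kept, would count the 4 / 2.5 case once under ALT grade 2 and once under bilirubin grade 2, with no link between the counts. Restoring that table resolves the contradiction but does not show the combination.

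**5. Other triggers below the listing**

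ALP > 2 to 2.5 x ULN is a Table 16-1 trigger but only grade 1. With abnormal baseline, ALT or AST > 2 x baseline is a trigger, and up to 3.0 x baseline it is also grade 1.

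**6. Scale**

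SAP 1.1 gives 20 randomized, one of them mis-randomized and by definition untreated: 20 - 1 = 19 treated at most.

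**The case against.** The strongest reply is that 2.8.3.3 is a specific rule limiting a general one, in an abbreviated report of a halted trial, and that its heading suggests it was meant to remove only a separate transaminase table. That is plausible, but the sentence does not say so, and 2.8.3.1 carries no matching exception. Nor do small numbers single out the liver: they apply equally to the hematology, electrolyte and renal rows kept in Table 5-1 and to the QTcF categories kept in SAP 2.8.4.1.1.

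The adverse event route is a real backstop. Protocol 8.4.3 requires clinically significant chemistry results to be reported on the laboratory page and as adverse events, and SAP 2.8.1 displays all adverse event information by participant. The backstop depends on the investigator's judgement of significance. Protocol 8.3.3 also keeps events clearly consistent with disease progression out of the adverse event record. The items that Protocol 10.1.1 asks for do not include the laboratory values, so the ALT/bilirubin pair need not be visible there.

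It is also fair that Protocol 12.5.1 plans no Hy's Law output and that Appendix 2 is labelled as suggested guidance. A joint flag is therefore an addition to the plan. However, the protocol's listing of all laboratory data would have let a reader find the pair among the recorded results, and the SAP narrowed it.

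Two limits on the evidence stand. Part of SAP 2.8.3.1 is redacted. SAP 2.1.1.7 also names chemistry among the endpoints summarized by visit. A by-visit group summary would neither identify a participant nor pair two tests.

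A reader might infer that the listing cannot catch a potential Hy's Law case at all. The documents do not support that: any case with ALT/AST > 5 x ULN or bilirubin > 3 x ULN shows at least one listed result. A reader might also infer that a grade 2/grade 2 case would appear in no table. On a literal reading its bilirubin still counts in the 2.8.3.1 table.

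**Conclusion.** The contradiction is in the current text and must be reconciled. It covers ALT, AST, GGT and ALP on a literal reading. If 2.8.3.3 is followed, the laboratory output visibly left for these enzymes in SAP 2.8.3 is the grade 3-4 listing. That listing can miss a potential Hy's Law case and is not designed to pair the two tests.

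The gap is bounded: normal baseline, ALT/AST peaking above 3 and up to 5 x ULN, and bilirubin above 2 and up to 3 x ULN, with the protocol's ALP condition met. How often such a case would occur cannot be derived from the documents. Expressing one missed case as a share of an arm would need arm sizes, which are not given.

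The conclusion assumes that the redacted part of 2.8.3.1 contains no liver listing that closes the gap. The point should be corrected because it decides which liver results are reported. It does not touch the efficacy analysis.

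**What to change.** - Delete SAP 2.8.3.3, or limit it expressly to a separate threshold table.
- State in 2.8.3.1 that the liver rows of Table 5-1 stay in the summary of new or worsening abnormalities.
- Add one participant-level listing, all visits, of the ALT, AST, ALP and total bilirubin values on the CRF for anyone meeting a Table 16-1 laboratory trigger that can be derived from collected data. Include ALT or AST > 3 x ULN with total bilirubin > 2 x ULN, and show ALP where available.

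The listing should say what it cannot show. INR is not in the scheduled panel (Protocol Table 8-2), so the INR trigger may not be derivable. Normal results may not have been entered (SAP 2.8.3), so a normal ALP may be absent. GGT is also not in the scheduled panel, so its row in the summary may be empty.

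The cost is a sentence or two of SAP text and one short listing for at most 19 participants, from values already recorded, with no new data collection.
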